6.1. General points and methodology

✓ Methodology — trial design

Prospective, multicenter, randomized, controlled, open-label study, with blind evaluation of the primary criterion and several secondary criteria (PROBE design).

Parallel group design (1:1):

- The arm receiving the device under investigation: PA1704
- The arm receiving the comparator medical device: BioRoot™ RCS.

✓ Measures to reduce or avoid bias.

Randomization and stratification:

Before the trial is set up, the CRO's biostatistician will computer-generate a block randomization list stratified by clinical indication (initial endodontic treatment (ET) versus re-treatment (ER)). The randomization system will be integrated directly into the electronic CRF.

Randomization will be carried out by the electronic CRF once the eligibility criteria have been checked, the clinical indication (ET or ER) has been determined and all this information has been recorded in the specific module by the investigator.

It should be noted that the proportion of ERs will be 30% of the overall sample, which is close to the rate reported in a French Health Insurance survey (Masson 2002). The rate of ER may vary between sites: some investigators, because of their specialty in endodontics, will include a majority of patients with an indication for re-treatment, whereas GP investigators will probably have more indications for first-line treatment.

Blind:

Investigators and patients will not be blind to the medical device allocated due to the different ways in which the 2 products are presented and used. On the other hand, two independent qualified assessors (previously calibrated under the supervision of the study coordinator) will conduct the blind, centralized review of the retro-alveolar X-rays taken at TO (reference radiograph obtained immediately post-operatively), 6 months, 12 months, 24 months, 3.5 years and 5 years (Refer to Section "Equipment to be used to evaluate clinical trial variables and arrangements for monitoring maintenance and calibration." section of this chapter); they will be blinded to centre, patient, indication (initial or repeat endodontic treatment), and treatment arm; the files will first be anonymized by the CRO.

✓ Outcome measures

Primary criterion (composite criterion):

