The primary criterion is the **2-year efficacy rate of endodontic treatment** based on radiological criteria assessed blind by independent reviewers (complete healing, reduction of lesions, failure) AND clinical criteria assessed by the investigator (tooth functionality and pain).

Secondary criteria:

Reminder of secondary objectives	Secondary outcome measure	Time of evaluation (assessor)
Evaluation of the 6-month efficacy rate determined on the basis of radiological and clinical criteria	Radiological criteria (complete healing, reduction of lesions, failure) AND clinical criteria (tooth functionality and pain)	6 months (radiological criteria assessed by blind reviewers; clinical criteria assessed by investigator)
Evaluation of the 12-month efficacy rate based on radiological and clinical criteria	Radiological criteria (complete healing, reduction of lesions, failure) AND clinical criteria (tooth functionality and pain)	12 months (radiological criteria assessed by blind reviewers ; clinical criteria assessed by investigator)
Assessment of the 3.5-year efficacy rate of the endodontic treatment determined on the basis of radiological and clinical criteria (PA1704 arm only)	Radiological criteria (complete healing, reduction of lesions, failure) AND clinical criteria (tooth functionality and pain)	3.5 years ± 6 months (radiological criteria assessed by reviewers blind to the centre; clinical criteria assessed by the investigator)
Evaluation of the 5-year efficacy rate on the basis of radiological and clinical criteria (PA1704 arm only)	Radiological criteria (complete healing, reduction of lesions, failure) AND clinical criteria (tooth functionality and pain)	5 years ± 6 months (radiological criteria assessed byreviewers blind to the centre; clinical criteria assessed by the investigator)
Radiological evaluation of the quality of the apical filling (in terms of the level of apical filling, density and resorption of the extruded material)	Level of obturation at the X-ray apex (complete obturation, under-filling or over-filling)	T0 immediate post-op (investigator)
	Density: radiopacity and presence of vacuity	T0, 6 months, 12 months, 24 months for the 2 arms, And 3.5 years, 5 years for the PA1704 arm. (investigator + blind reviewer)
	Resorption of extruded material in the periapical space in the event of over-filling	6 months, 12 months, 24 months for the 2 arms, And 3.5 years, 5 years for the PA1704 arm. (investigator + blind reviewer)

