Measurement time and people in charge of evaluation:

For each criterion, this information is given in the table above.

Generally speaking, the assessment of performance and safety criteria begins with the root canal obturation.

Method of evaluating the efficacy rate of initial or repeat endodontic treatment (at 6 months, 12 months and 24 months for the 2 arms; and 3.5 years and 5 years for the PA1704 arm):

Therapeutic efficacy is a composite criterion based on the radiological data assessed **in blind conditions** by reviewers AND on the clinical data assessed **in an open-label manner** by the investigator at the follow-up visits at 6 months, 12 months, 24 months, 3.5 years and 5 years (only the PA1704 arm for the last 2 visits). With regard to the blind evaluation of the radiological criteria by two independent reviewers, the following clarifications are provided:

- The reviewers shall examine the anonymized retro-alveolar images (JPEG files as described in the imaging procedure in section "Equipment to be used to evaluate clinical trial variables and arrangements for monitoring maintenance and calibration." of this chapter) and answer the following questions:
 - Apical lesion: 1) Presence, absence or appearance of a lesion compared with the TO reference image? 2) In the case of a pre-existing lesion at TO, what is the evolution of the size of the lesion (reduction, stabilization or increase)?
 - Root canal filling density: 1) Is the radiopacity sufficient? 2) Presence of at least one bubble in the filling material?
 - Resorption of extruded material where applicable: Is the extruded material still present in the apical space?
- Timetable: 5 centralized image review campaigns are planned, one before each statistical analysis:
 - o 1st review campaign: At the end of the 6-month follow-up of all enrolled patients, a blind review of the T0 reference image and the 6-month follow-up image,
 - o ^{2nd} campaign: after 12 months' clinical follow-up of all patients, blind review of the 12-month check-up image,
 - o 3rd campaign: After 24 months of clinical follow-up for all patients, a blind review of the 24-month check-up image,
 - 4th campaign: After approximately 3.5 years of clinical follow-up of the patients treated with the PA1704 MD, a centre-blind review of the 3.5-year follow-up image,

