	 irrigation solution, then dry without completely dehydrating the root canal. 4. Open the protective bag and take out the syringe. Make a note of the patient identifier on the label. 5. Use the endodontic tip supplied with the PA1704. 6. Remove the syringe cap and screw on an endodontic tip as far as it will go. 	 4. Prepare BioRoot™ RCS according to the mixing instructions above. 5. Slowly enter the canal, applying a layer of BioRoot™ RCS to the canawalls using the gutta-percha cone or lentulo spiral (do not exceed 600 800 rpm). 6. Complete the filling procedure by inserting the master gutta-perchange. 					
7. The gripping wing can be placed on the syringe to make it							
		easier to squeeze the plunger.					
	8. Before injecting the cement into the canal, check that the cement comes out of the syringe by ejecting a small quantity of						

material; if the syringe is blocked, do not use it, dispose of it in the syringe collection box and complete the defect form in the eCRF.

- 9. Insert the tip into the canal, up to a maximum of the first third of its length; check that the tip is not stuck in the canal or being forced in, then gently inject the material, without forcing it, and gradually and slowly withdraw the tip from the canal while continuing to inject the material.
- 10. Complete the filling procedure by inserting the master gutta-percha cone (single cone technique) or several gutta-percha cones (lateral condensation technique) to the length of the working area.
- 11. Assess the quality of the root canal filling by taking an X-ray (intraoperative check),
- 12. Cut the cone with a heat source at the entrance to the filled canal.
- 13. Complete the procedure by lightly condensing the upper part of the gutta cone with a large-diameter vertical endodontic compactor
- 14. Assess the quality of the root canal filling by taking an X-ray (intraoperative check) at TO.
- 15. Create a watertight coronal restoration (see below).
- 16. If it is necessary to fit an anchor pin, this should be done after the PA1704 material has fully cured in the canal, i.e. 7 days.

- 8. Cut the cone with a heat source at the entrance to the filled canal.
- 9. Complete the procedure by lightly condensing the upper part of the gutta cone with a large-diameter vertical endodontic compactor
- 10. Assess the quality of the root canal filling by taking an X-ray (intraoperative check) at TO.
- 11. Create a watertight coronal restoration (see below).

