- **Randomization** of the medical device (PA1704 or BioRoot™ RCS) stratified according to endodontic treatment indication (randomization system integrated in the eCRF).
- **Endodontic treatment** over 1 or 2 sessions, depending on the usual practice of each practitioner and the clinical situation (initial or repeat endodontic treatment) and following the instructions for use of the PA1704 or BioRoot™ RCS filling materials (see instructions above).

Record of data describing operating procedures in the eCRF: 1) preparation of the canal (technique for removing the old material in the event of re-treatment), 2) shaping and cleaning of the canal (instruments used, irrigation solutions and techniques, rinsing solution, drying), 3) number of gutta-percha cones used and condensation technique.

- Immediate post-operative X-ray check (=T0; reference image for patient follow-up; reminder: the entire tooth from the *crown to the apex, including the root* must be visible in the image):
 - Evaluation of the level of obturation at the X-ray apex for each canal,
 - Evaluation of obturation density (radiopacity and presence of voids),
 - Upload the T0 image to the eCRF.
- **Quality coronal restoration**: the reconstruction can be either temporary or permanent if the conditions are right and according to the practitioner's habits. In all cases, the restoration must be watertight and made using glass ionomer cement or a composite (see recommendations above). Exclusive endodontic investigators must ensure watertight reconstitution.
- Explanations and handing over of the **patient record** for recording pre-operative and post-operative pain over 7 days, painkillers and AEs. The preoperative and T0 VAS is completed in the office in the presence of the dental surgeon or dental assistant in order to check that the evaluation tool has been properly understood; it should be noted that if the root canal preparation and filling are carried out over 2 sessions, preoperative pain levels will be recorded at the beginning of each session).
- Scheduling the **next consultation**: either the V2 visit to perform the standard permanent coronal restoration (if the restoration was temporary at V1 i.e. within 45 days), or the V3 follow-up visit at 6 months if the permanent coronal restoration was performed at V1.

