In addition, the difference in the 2-year efficacy rate between the 2 materials are to be calculated; its unilateral confidence interval of 95% will be provided and the lower limit is will be compared against the non-inferiority limit.

The main performance analysis will be carried out on the PP population, in accordance with the recommendations for non-inferiority studies. This will be complemented by an analysis of the mITT population to check the stability of the results.

7.7.5. Analysis of secondary performance criteria:

Efficacy rate at 6 months based on radiological and clinical criteria: Description and comparison, between the PA1704 arm and the BioRoot™ RCS arm, of the 6-month efficacy rate by Pearson's Chi-2 test or Fisher's exact test.

Efficacy rate at 12 months based on radiological and clinical criteria: Description and comparison, between the PA1704 arm and the BioRoot™ RCS arm, of the 12-month efficacy rate by Pearson's Chi-2 test or Fisher's exact test.

Quality of apical obturation at T0 (complete obturation, under-filling or over-filling): Description and comparison, between the PA1704 arm and the BioRoot™ RCS arm, of the proportions of apical obturation quality by Pearson's Chi-2 test or Fisher's exact test.

Density of root canal filling at T0, 6 months, 12 months, 24 months: Description and comparison at each time point, between the PA1704 arm and the BioRoot™ RCS arm, of the proportions of canals with an

obturation density deemed sufficient and the proportions of canals free of voids, by Pearson's Chi-2 tests or Fisher's exact tests.

Progress of material resorption over 24 months, in the event of over-filling at T0 (6 months, 12 months and 24 months): Description and comparison, between the PA1704 arm and the BioRoot™ RCS arm, of the proportions of patients with resorbed materials among patients who were over-filled at T0 by Pearson's Chi-2 test or Fisher's exact test.

Pre-operative and post-operative pain experienced by the patient (VAS 0-100 mm) at T0 (end of surgery), 12h, 24h, 48h, 72h and 7 days: For each time point, description and comparison of the pain, between the PA1704 arm and the BioRoot™ RCS arm, by a Student, Welch or Wilcoxon test. A figure representing average pain as a function of assessment times per arm will be provided. The causes of the pain will be described.

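### Resorption of extruded sealer is tested between arms only in patients over-filled at T0, a post-randomisation subset, so the test is not protected by randomisation and may be biased in either direction

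*Combined protocol and SAP*

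**What the plan says.** Section 7.7.5 lists a secondary criterion, "Progress of material resorption over 24 months, in the event of over-filling at T0 (6 months, 12 months and 24 months"), and compares the arms in terms "of the proportions of patients with resorbed materials among patients who were over-filled at T0 by Pearson's Chi-2 test or Fisher's exact test". It does not call this comparison exploratory or note that it is non-randomised. It gives no version with all treated patients in the denominator.

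Four other places bear on it:

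- **Timing.** Section 6.5.2 places over-filling at the "Immediate post-operative X-ray check (=T0; reference image for patient follow-up"), which follows randomisation and filling at visit V1.
- **Who decides.** Table 3 in section 6.1 assigns the level of obturation to "T0 immediate post-op (investigator"). The same section says "Investigators and patients will not be blind to the medical device allocated due to the different ways in which the 2 products are presented".
- **How the sealers are placed.** Table 5 tells the operator to "gently inject the material, without forcing it, and gradually and slowly withdraw the tip from the canal while continuing to inject the material" for PA1704. BioRoot RCS is carried onto the canal walls with the cone or a lentulo spiral.
- **Over-filling as an outcome.** Section 7.7.5 also plans: "Quality of apical obturation at T0 (complete obturation, under-filling or over-filling): Description and comparison" between the arms.

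The blind reviewers' form in section 6.1 asks: "Resorption of extruded material where applicable: Is the extruded material still present in the apical space".

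**The concern.** Randomisation makes the arms comparable in everyone who was randomised. It gives no such guarantee in a subset defined by something that happens afterwards and that the allocated treatment can affect. Over-filling at T0 is such an event. If one sealer, or its way of delivery, over-fills teeth that the other would not, the over-filled group in that arm contains a different mix of extrusions. Its resorption rate can then differ even if the sealer has no effect on resorption. Classification by an unblinded investigator gives allocation a second route into the subset.

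There is also a gap. A reader comparing the sealers wants to know how many treated patients still have material beyond the apex at follow-up. No planned analysis compares that between arms. Section 4.4 links over-filling to pain and to compression of the periapical tissues, with possible altered sensation, and section 3.3 says this is the first use of PA1704 in humans. A resorption test with an unclear meaning is therefore worth correcting, although it is a secondary criterion.

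**Working it through.** **The plan's own figures.** The plan gives none for this comparison: no over-filling rate, no resorption rate, no power. The only sample size is for the primary test (section 7.2: 90% in both arms, margin 13 points, one-sided 5%, power 80%): n = (1.645 + 0.842)² × 2 × 0.90 × 0.10 / 0.13² = 65.9, so 66 per group, which reproduces. It is used below only as a plausible number evaluable per arm, with 80 as the number enrolled. **Every rate from here on is an assumption.**

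**1. Two quantities that can point different ways.** Take 80 per arm, with 30 over-filled and 15 resorbed under PA1704, and 10 over-filled and 4 resorbed under BioRoot RCS.

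| Comparison | PA1704 | BioRoot RCS | p |
|---|---|---|---|
| Resorbed among over-filled (planned) | 15/30 = 50% | 4/10 = 40% | Fisher 0.72 |
| Over-filled at T0 (planned, separate) | 30/80 = 37.5% | 10/80 = 12.5% | Pearson 0.0003 |
| Material still present, all patients (not planned) | 15/80 = 18.8% | 6/80 = 7.5% | Pearson 0.035, Fisher 0.059 |

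In row 1 the smallest expected count is 10 × 21/40 = 5.25 for not resorbed and 10 × 19/40 = 4.75 for resorbed. The second is below 5, so section 7.7.3 calls for Fisher. In row 3 the smallest expected count is 80 × 21/160 = 10.5, so it calls for Pearson. With 66 per arm and similar rates (12/66 v 5/66), Pearson gives p = 0.069. The third row is therefore a modest difference and not a robust one.

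This table shows two estimands diverging. On its own it does not show selection bias, because a larger denominator does not bias a proportion.

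**2. Selection bias, with no sealer effect on resorption.** Suppose a share a of teeth over-fills with either sealer and resorbs with probability rA. A further share b over-fills with one sealer only and resorbs with probability rB. Then, for the sealer that extrudes more:

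- resorbed among over-filled = (a·rA + b·rB) / (a + b), against rA for the other sealer;
- material still present in all = a(1 − rA) + b(1 − rB), against a(1 − rA).

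With a = 15%, rA = 40%, rB = 80%:

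- b = 10%: (0.06 + 0.08)/0.25 = 56% v 40% resorbed; 0.09 + 0.02 = 11.0% v 9.0% still present.
- b = 15%: (0.06 + 0.12)/0.30 = 60% v 40% resorbed; 0.09 + 0.03 = 12.0% v 9.0% still present.

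The sealer that extrudes more looks 16 to 20 points better on the planned test and is 2 to 3 points worse over all patients.

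**3. The direction is not fixed.** With a = b = 20% and rA = 40%:

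| rB | Resorbed among over-filled | Still present, all patients |
|---|---|---|
| 80% | 60% v 40% | 16% v 12% |
| 40% | 40% v 40% | 24% v 12% |
| 20% | 30% v 40% | 28% v 12% |

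The planned test favours the sealer that extrudes more, is neutral, or goes against it, depending only on an unknown rB.

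**4. Size of the subset.** If 20% of 66 are over-filled (13 per arm), exact Fisher power to detect 40% v 80% resorbed is 46%. With 13 v 26 over-filled it is 62%.

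**The case against.** The strongest reply has four parts.

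*The plan already compares over-filling at T0 in both arms.* This stands. In the illustration that test gives p = 0.0003 against PA1704, beside a null resorption result. A reader might infer that the plan as a whole would hide a sealer that extrudes more, or make it look better. The documents do not support that, because the over-filling difference would be reported. But the T0 test neither makes the conditional test a randomised one nor measures what remains at 24 months.

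*Resorption has meaning only where something was extruded, and that is the stated objective (sections 5.1 and 6.1).* This stands as an argument for reporting the conditional proportion. It does not justify an unqualified test between arms. Persistence can be approximated from planned tables, as the over-filling rate times the share not resorbed, but it would come without an interval or a planned comparison.

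*The sealer is not the only cause.* A reader might infer that the sealer itself creates the subset, or that PA1704 extrudes more. Section 4.4 lists over-filling under mechanical canal treatment as well as under the filling stage, section 6.2 leaves technique to the practitioner, and no rate for either device is given. What stands is that over-filling comes after randomisation and is open to influence by arm.

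*Harms are captured elsewhere.* Sections 7.6 and 7.7.6 compare adverse events and extra consultations over all treated patients. This limits the consequence. It does not answer the radiological question.

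**Conclusion.** The concern holds for a secondary criterion. The planned resorption test conditions on a status that arises after randomisation, that allocation can influence, and that an unblinded investigator assigns. Its result cannot be read as a randomised comparison of the sealers. The bias may run in either direction, and the documents do not allow its size to be estimated. In the assumed scenarios, the conditional comparison moved by −10 to +20 points with no sealer effect on resorption, while persistence over all patients was higher each time for the sealer that extrudes more. The T0 comparison would reveal differing over-filling rates, so the weakness lies in one test and one missing comparison, and the account of extrusion as a whole is not misleading. The primary non-inferiority conclusion does not depend on this.

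**What to change.** In section 7.7.5 and the SAP:

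1. Make the between-arm comparison the proportion of patients with extruded material visible at 6, 12 and 24 months. Analyse all treated patients with a readable image, by randomised arm, with teeth showing no extrusion counted as 'no'. Give the difference with a 95% CI.
2. Have the blind reviewers answer the existing extruded-material question for every image they read, including T0, and drop the restriction to applicable cases. Otherwise the unblinded T0 classification passes into the new endpoint through the patients counted as 'no'.
3. Keep the proportion resorbed among patients over-filled at T0, which is the stated objective, as a description per arm without a test. Print it beside the over-filling rate.
4. Report the number without a readable image per arm and visit, since section 7.7.11 plans no imputation.

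The cost is one more answer per image already reviewed, a small change to the review form, and the loss of a subset test that would have had low power. No new visit or X-ray is needed.
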